2.1 Overall Objective

We aim to explore the safety and efficacy of Compound Zhenzhu Tiaozhi capsules in the treatment of non-alcoholic fatty liver disease (NAFLD) through a prospective, open-label, and randomized clinical study. We also expect to prevent the progression of simple hepatic steatosis to non-alcoholic steatohepatitis (NASH), and expect to improve the efficacy of NAFLD treatment, while reducing the incidence of liver cirrhosis and hepatocellular carcinoma. We will then explore the mechanism of action of Compound Zhenzhu Tiaozhi capsules for the treatment of NAFLD.

2.2 Primary Objectives

1. To explore the safety and efficacy of Compound Zhenzhu Tiaozhi capsules for the treatment of NAFLD, compared with metformin and simvastatin.
2. To summarize the regularity of disease progression in the development of NAFLD.
3. To promote the therapeutic options of NAFLD and to improve long-term efficacy.
4. To explore the potential mechanism of Compound Zhenzhu Tiaozhi capsules for the treatment of NAFLD.

[figure not shown]
2.3 Secondary Objectives

1. To evaluate the change in intestinal mucosal barrier function by detecting biochemical parameters of the intestinal mucosal barrier; to analyze the relationship between NAFLD and the function of the intestinal mucosal barrier.
2. To explore the trends of small intestinal bacterial overgrowth (SIBO) during the treatment process.
3. To investigate whether lipid profiles and liver biochemical parameters are improved following treatment with Compound Zhenzhu Tiaozhi capsules.
4. To assess whether insulin resistance is improved following treatment with Compound Zhenzhu Tiaozhi capsules.
5. To monitor adverse events and put forward specific solutions for the adverse events.

3. Design, evaluation, and plans

3.1. Design

This is a prospective, open-label and randomized clinical study.

[figure not shown]

Group 1: treatment with Compound Zhenzhu Tiaozhi capsules

Group 2: treatment with simvastatin

Group 3: treatment with metformin

Group 4: TLC (transform life custom)

ALT, alanine transaminase; ASCVD, atherosclerotic cardiovascular disease

Biochemical tests include routine blood test, liver function tests including measurement of transpeptidases, uric acid, FBS (fasting blood glucose), FINS (fasting insulin), and lipid profiles.

Physical examinations include waist circumference, hip circumference, blood pressure, heart rate, and body mass index (BMI).

Imaging include abdominal color doppler ultrasound, and Fibrotouch

3.2 The Method of Random Assignment

Newly diagnosed patients who meet the inclusion criteria will have a case number according to their order of enrollment (for example: case number of the first patient: 001, second patient: 002). They

will then obtain the corresponding therapeutic regimens based on their case number with 1:1:1:1 ratio randomized tables.

3.3 Random Numbers

Researchers will screen subjects based on the established inclusion and exclusion criteria first, and then assign the case number to the enrolled subjects based on their order of enrollment. Secondly, the enrolled subjects will obtain their corresponding therapeutic regimens based on the assigned case number. Thirdly, researchers will record the case number and therapeutic regimens for each subject in each case report form. The case number for each subject will not change during the entire study.

3.4 Sample Size

A total of 196 patients will be enrolled in this study. The sample size is estimated as follows:

Previous studies have reported that the efficiency rate of metformin and simvastatin in the treatment of NAFLD is 36-52%. We hypothesize that the efficiency rate of Compound Zhenshu Tiaozhi capsules will increase by 25% compared to standard drugs.

Statistical calculation: $P_1 = 69\%$, $P_2 = P_3 = 44\%$, $P_4 = 10\%$, $\delta = P_1 - P_2 = 25\%$, with $\alpha = 0.05$,

power = 0.80, and a bilateral test, $n = \frac{\chi_{\alpha}^2 + \chi_{\beta}^2}{w^2}$, of which $w = \sqrt{\sum_{i=1}^m \frac{(P_{t,i} - P_{c,i})^2}{P_{c,i}}}$, thus n will be equal to 44.

Assuming that the rate of loss to follow up is 10%, each group will require 49 cases. Therefore, a total of 196 cases will be required for the four groups.

4. Evaluation of the Efficacy of Parameters and Predictors

4.1 The Primary Efficacy Parameters

Fat attenuation index: The fat attenuation index will be used to assess the therapeutic efficacy. A normal fat attenuation index is defined as < 240 db/m, mild is 240-264 db/m, moderate is 265-294 db/m, and severity is > 295 db/m. We will detect the fat attenuation index at 0, 1, 3, 6 months following treatment. Effective: fat attenuation index is reduced by a level or more (example: moderate to mild). Invalid: fails to meet the effective standard.

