#### 2. Enrollment:

The subjects will be enrolled following the design of a prospective study. The inclusion criteria will be strictly in accordance with the diagnostic criteria of simple steatosis and NASH, as stipulated in the *Chinese Guidelines for the Diagnosis and Treatment of Nonalcoholic Fatty Liver Disease (Revised version 2010)*. The subjects should have a diagnosis of simple steatosis or NASH (age distribution: 18 to 75 years old), with serum alanine transaminase (ALT)  $\leq 2$  times the upper limit of normal, with no other chronic liver diseases or serious complications in other organs, with no malignant tumors.

2.1. Diagnostic Criteria of NAFLD (2010): NAFLD can be diagnosed if the following items 1–4, plus item 5 or item 6 are present:

- i. No alcoholic history (alcohol consumption  $< 140$  g/week for male; or  $< 70$

g/week for female);

- ii. No other diseases that can lead to fatty liver, such as viral hepatitis, drug-induced liver disease, total parenteral nutrition, hepatolenticular degeneration diseases, or autoimmune liver diseases;
- iii. Overweight and/or visceral obesity, hyperglycemia, dyslipidemia, hypertension and other metabolic syndrome;  
Serum transaminase and GGT levels are normal or elevated to a mild to moderate degree;
- iv. Liver imaging findings show diffuse hepatic steatosis;
- v. A liver biopsy meets the histologic diagnostic criteria of fatty liver diseases;

2.2. Diagnostic criteria of simple steatosis: Simple steatosis can be diagnosed if the following item 1-2, plus item 3 or item 4 are present.

- i. Presence of item 1-3 of the clinical diagnosis criteria of NAFLD;
- ii. Liver biochemical tests are normal (blood biochemical analysis);
- iii. Liver imaging findings meet the diagnostic criteria for hepatic steatosis (Fibro touch test);
- iv. A liver biopsy meets the histologic diagnostic criteria for simple hepatic steatosis.

2.3. The diagnostic criteria of NASH: NASH can be diagnosed with the following items 1 to 3 or item 4.

- i. Presence of items 1–3 of the clinical diagnosis criteria of NAFLD;
- ii. Serum ALT levels are persistently elevated for more than 4 weeks;
- iii. Liver imaging findings show diffuse hepatic steatosis;
- iv. A liver biopsy meets the histologic diagnostic criteria for NASH.

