### 4. Endpoints:

#### 4.1 Primary endpoints

*Fat attenuation index:* The fat attenuation index will be used to assess the therapeutic efficacy. A normal fat attenuation index is defined as < 240 db/m, mild is 240-264 db/m, moderate is 265-294 db/m, and severity is > 295 db/m. The investigators will detect the fat attenuation index at 0, 1, 3, 6 months following treatment. Effective: fat attenuation index is reduced by a level or more (example: moderate to mild). Invalid: fails to meet the effective standard.

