4.4 Predictors

Univariate and multivariate statistical analyses will be used to analyze therapeutic efficiency.

1. Factors considered for univariate analysis are as follows:

- a. Baseline: life style, gender, age, baseline liver biochemical parameters, baseline fat attenuation index, baseline lipid profiles, baseline quality of life, baseline BMI;
- b. Factors relevant to treatment: dose of medication, insulin resistance, intestinal barrier function, SIBO.

2. Factors considered in multivariate analysis are as follows:

Only factors that have statistical significance in univariate analysis will be entered for multivariate analysis. Additional three factors including insulin resistance, intestinal barrier function, and intestinal bacterial overgrowth will still be considered for multivariate analysis, regardless of univariate analysis results.

5. Definitions

Diabetes: fasting blood glucose ≥ 7.8 mmol/L, or two hours post-75 g glucose drink/or postprandial random glucose ≥ 11.1 mmol/L.

Overweight: BMI > 28 (kg/m²); obese: BMI > 31 (kg/m²); BMI = weight/height² (kg/m²)

Liver biochemical parameters: Detect liver injury and liver excretion function at time of admission and 6 months later.

NAFLD Fibrosis score (NFS): This is a noninvasive method to evaluate liver fibrosis, and is calculated by six variables such as age, BMI, and platelet count. The formula is as follows: $-1.675 + (0.037 \times \text{age}) + (0.094 \times \text{BMI}) + (1.13 \times (\text{hyperglycemia or diabetes; yes} = 1, \text{no} = 0)) + (0.99 \times \text{AST} / \text{ALT}) - (0.013 \times \text{platelet count (x } 10^9 / \text{L)}) - (0.66 \times \text{albumin (g / dL)})$. A score less than -1.455 is used to rule out advanced liver fibrosis.

SIBO: Due to small intestinal stasis, bacteria overgrow in the small intestine, resulting in several clinical symptoms such as malabsorption, diarrhea, anemia, and nutrient absorption disorders. Appropriate use of antibiotic can achieve beneficial effects.

Intestinal barrier function test: detect DAO, D-lac, and LPS, and combine with clinical manifestations to evaluate the function of intestinal mucosal barrier.

SF-36 assessment: SF-36 can comprehensively assess the quality of life from multiple dimensions, and is now widely applied in the evaluation of quality of life, clinical trial results, and clinical efficacy.

6. Definitions of Data Sets

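### Whether a patient counts as 'Effective' depends on where in the band they start, yet baseline fat attenuation index is not a guaranteed covariate and 295 dB/m has no band; the cost is modest precision, not bias

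*SAP*

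**What the plan says.** Protocol IV.4.1 and SAP 4.1 share one set of bands for the fat attenuation index ('the index' below): normal under 240 dB/m, mild 240-264, then "moderate is 265-294 db/m, and severity is > 295 db/m". The index is measured at months 0, 1, 3 and 6. Success is defined as "Effective: fat attenuation index is reduced by a level or more (example: moderate to mild", and anything else as "Invalid: fails to meet the effective standard".

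SAP 4.4 (Predictors) puts the starting value in its list of univariate candidates: "baseline liver biochemical parameters, baseline fat attenuation index, baseline lipid profiles". It then applies a screen: "Only factors that have statistical significance in univariate analysis will be entered for multivariate analysis". Three factors are considered whatever the screen shows: insulin resistance, intestinal barrier function and bacterial overgrowth. Baseline index is not among them, and treatment arm is not a listed factor.

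Protocol IV.4.4 compares intrahepatic fat between arms at each visit and names no covariate. Protocol 3.2 and SAP 3.2 describe 1:1:1:1 randomisation tables without stratification by the index. SAP 6.2 points to the per-protocol set as the main set for primary efficacy.

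**The concern.** Two patients with the same true improvement can be classed differently only because one started just above a cut-off and the other near the top of the band. Baseline index is thus built into the endpoint and is a strong predictor of it. If the arm comparison ignores it, predictable variation stays in the error term and the trial loses some power. If its use is left open, the choice may be made after results are known.

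Two boundary cases also need wording. A reading of exactly 295, at baseline or follow-up, cannot be classified. A patient who starts below 240 has no lower band to reach and can only be 'Invalid'. The Fibro touch route to simple steatosis probably keeps such patients out. The other entry routes in Protocol IV.2.2 and IV.2.3 state no minimum index: "A liver biopsy meets the histologic diagnostic criteria for simple hepatic steatosis", "Liver imaging findings show diffuse hepatic steatosis" (NASH) and "A liver biopsy meets the histologic diagnostic criteria for NASH".

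**Working it through.** **1. The plan's own figure.** SAP 3.4 gives 69% vs 44%, two-sided 0.05, power 0.80 and n = 44 per arm. With mean proportion 0.565, the usual formula is

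n = [1.96·√(2·0.565·0.435) + 0.8416·√(0.69·0.31 + 0.44·0.56)]² / 0.25² = (1.3742 + 0.5710)² / 0.0625 = 60.5, so 61.

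The stated 44 does not reproduce two-sided. The later steps do: 44/0.9 = 48.9, so 49, and 4 × 49 = 196. Unadjusted power at 44 is Φ[(0.25·√44 − 1.3742)/0.6785] = Φ(0.42) = 66%; at 49 it is Φ(0.55) = 71%. That shortfall is a separate matter. Here it is only the starting point, and it shows that precision is scarce.

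**2. Fall needed (documents only).** In whole dB/m, with b the baseline and t the lower edge of its band, the fall needed is b − t + 1:
- mild: 1 from 240, 25 from 264
- moderate: 1 from 265, 30 from 294
- severe (t taken as 295): 2 from 296, 56 from 350

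**3. Chance of 'Effective' with no true change (assumed change SD c = 25 dB/m).** Centred on the observed baseline it is Φ((t − b)/c). With regression to an assumed mean of 295 and total SD S, take ρ = 1 − c²/(2S²), conditional mean 295 + ρ(b − 295) and SD S·√(1 − ρ²).

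| Baseline | No regression to the mean | S = 25 | S = 35 |
|---|---|---|---|
| 266 | 48% | 24% | 36% |
| 290 | 16% | 10% | 13% |
| 297 | 47% | 48% | 48% |
| 340 | 4% | 15% | 8% |

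Example: from 290, Φ((265 − 290)/25) = Φ(−1) = 16%. A real effect does not remove the dependence. With a mean fall of 20 and SD 20, the chance is 84% from 265 and 33% from 294; with SD 40 it is 69% and 41%. The pattern is saw-toothed, so a straight-line baseline term captures only part of it.

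**4. Bias and variance.** These are 20,000 simulated trials per setting: 44 per arm, true difference 0.25, assumed baseline mean 290 with SD 25 or 35, limited to 240 or more, and change SD 20 or 30. The unadjusted difference averages 0.248-0.251, and −0.003 to 0.001 under the null, so there is no bias. Its standard error is 0.102-0.103. A linear baseline term gives 0.097-0.102 (variance 1-11% lower). Distance above the band's lower edge gives 0.092-0.099 (7-19% lower).

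**5. Power.** This uses 22 settings at 44 per arm: assumed baseline mean 295, SD 25 or 35, truncated at 240; change SD 20, 30 or 40; with and without regression to the mean; month 6 taken as the endpoint visit. 'Mixed' means that a fraction falls by 60 dB/m and the rest by 0. Unadjusted power is 64-68%. The adjusted test uses band and distance in a logistic model, reported as a standardised difference in proportions. Ranges span repeated simulation runs.

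| | Equal shift | Mixed |
|---|---|---|
| Nominal gain | about 3-13 points | about 1-5 points |
| Gain with adjusted test held at 5% | 1-12 points | 0-3 points |

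In three of the 11 mixed settings the size-corrected gain is below half a point. Simulated type I error of the adjusted test is about 5-7%, against 4.1-5.2% for the unadjusted test. At 49 per arm, in three equal-shift settings, nominal power rises from 72-74% to 73-80%.

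**The case against.** The case against is substantial. Every SD is assumed. Part of the nominal gain is only the adjusted test running above 5%, and with mixed response an honest comparison may show almost nothing. The 44 per arm is the number after loss; an analysis of everyone enrolled would be nearer 49, where unadjusted power is already 71-74%. The SAP text reviewed stops at 9.5 (Baseline characteristics), so a later efficacy section could name the covariate. The 295 gap is one label.

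All of this stands as a limit on size, and the last two points narrow the claim to the text as it reads. None of it alters the band arithmetic, the unclassified value or the absence of a guaranteed adjustment in that text.

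A reader might also take the SAP 4.4 screen as the rule governing the arm comparison. The text does not support that. The section concerns predictors and does not list arm. It shows that baseline index is unprotected there, not that the treatment test depends on the screen.

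**Conclusion.** The point holds as one of precision and wording, and it is worth acting on because the remedy is cheap. The dependence on starting position and the gap at 295 follow from the documents alone. The size of the gain rests on assumed SDs, on month 6 as the endpoint visit and on the pattern of response.

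Three stronger readings are not supported:
- **Bias between arms.** Assignment is randomised, so starting position is balanced in expectation, and the simulations show no bias. This covers the between-arm difference only. A response percentage within one arm includes patients near a cut-off who respond by noise.
- **A known power loss from patients below 240.** Entry is possible by some routes, but the documents give no share, so no loss can be calculated.
- **A reason to replace the endpoint.** An ANCOVA of month-6 index has more power, but mainly because it does not dichotomise. Without regression to the mean and with equal shift, it reaches 88-96%, and an unadjusted t-test of change already reaches 88-97%.

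**What to change.** 1. Label the top band 295 or more in Protocol IV.4.1 and SAP 4.1. If readings carry decimals, also close the gaps between 264 and 265 and between 294 and 295.
2. Keep 'Effective' as the primary endpoint, in whichever analysis set the plan names as primary; SAP 6.2 points to the per-protocol set, and this point does not decide that question. Always adjust the arm comparison for baseline band and distance to the next lower cut-off, with no significance screen. Report the standardised adjusted difference in proportions beside the raw percentages; it is on the scale of the 25-point difference in SAP 3.4.
3. Report by arm the number of patients with baseline index below 240, with a sensitivity analysis limited to 240 or more.
4. Optionally add an ANCOVA of month-6 index on arm and baseline index as a supporting analysis.

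**Cost:** SAP wording, one band label in two documents, and one or two regressions on data already planned; no new visit.

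**Downside:** the adjusted estimate relies on a model, and its type I error is about 5-7% at 44 per arm. Pre-specify a small-sample correction or a re-randomisation p-value. The latter must follow the actual allocation scheme, which the SAP should therefore state; the assignment sections mention no blocks.

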4.2 The Secondary Efficacy Parameters

(1) *Serum triglyceride*

(2) *Serum cholesterol*

(3) *Serum lipoproteins*: chylomicron (CM), very-low-density lipoprotein (VLDL), low-density lipoprotein (LDL), and high-density lipoprotein (HDL).

(4) *Hydrogen/methane breath testing*: breath testing for SIBO.

(5) *Intestinal mucosal barrier*: detect levels of diamine oxidase (DAO), D-lactic acid (D-lac), and lipopolysaccharide (LPS), and combine with the clinical manifestations to evaluate the function of the intestinal mucosal barrier.

(6) *Quality of life (SF-36 Scores)*: The quality of life of the patients before and after treatment will be assessed using SF-36 scores and compared to assess the improvement.

4.3 Safety

Safety profiling includes adverse events and serious adverse events, as well as vital signs and laboratory tests.

4.4 Predictors

Univariate and multivariate statistical analyses will be used to analyze therapeutic efficiency.

1. Factors considered for univariate analysis are as follows:

- a. Baseline: life style, gender, age, baseline liver biochemical parameters, baseline fat attenuation index, baseline lipid profiles, baseline quality of life, baseline BMI;
- b. Factors relevant to treatment: dose of medication, insulin resistance, intestinal barrier function, SIBO.

2. Factors considered in multivariate analysis are as follows:

Only factors that have statistical significance in univariate analysis will be entered for multivariate analysis. Additional three factors including insulin resistance, intestinal barrier function, and intestinal bacterial overgrowth will still be considered for multivariate analysis, regardless of univariate analysis results.

5. Definitions

Diabetes: fasting blood glucose ≥ 7.8 mmol/L, or two hours post-75 g glucose drink/or postprandial random glucose ≥ 11.1 mmol/L.

Overweight: BMI > 28 (kg/m²); obese: BMI > 31 (kg/m²); BMI = weight/height² (kg/m²)

Liver biochemical parameters: Detect liver injury and liver excretion function at time of admission and 6 months later.

NAFLD Fibrosis score (NFS): This is a noninvasive method to evaluate liver fibrosis, and is calculated by six variables such as age, BMI, and platelet count. The formula is as follows: $-1.675 + (0.037 \times \text{age}) + (0.094 \times \text{BMI}) + (1.13 \times (\text{hyperglycemia or diabetes; yes} = 1, \text{no} = 0)) + (0.99 \times \text{AST} / \text{ALT}) - (0.013 \times \text{platelet count (x } 10^9 / \text{L)}) - (0.66 \times \text{albumin (g / dL)})$. A score less than -1.455 is used to rule out advanced liver fibrosis.

SIBO: Due to small intestinal stasis, bacteria overgrow in the small intestine, resulting in several clinical symptoms such as malabsorption, diarrhea, anemia, and nutrient absorption disorders. Appropriate use of antibiotic can achieve beneficial effects.

Intestinal barrier function test: detect DAO, D-lac, and LPS, and combine with clinical manifestations to evaluate the function of intestinal mucosal barrier.

SF-36 assessment: SF-36 can comprehensively assess the quality of life from multiple dimensions, and is now widely applied in the evaluation of quality of life, clinical trial results, and clinical efficacy.

6. Definitions of Data Sets

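### SAP 4.4 picks predictors by univariable significance in the same patients, so the reported intervals and p-values of the screened factors are unreliable and moderate real predictors can be lost

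*SAP*

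**What the plan says.** SAP 4.4 (Predictors) plans univariable and then multivariable analyses of therapeutic efficiency. The univariable candidates come in two lists.

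- Baseline: "life style, gender, age, baseline liver biochemical parameters, baseline fat attenuation index, baseline lipid profiles, baseline quality of life, baseline BMI".
- Relevant to treatment: "dose of medication, insulin resistance, intestinal barrier function, SIBO".

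The rule for the multivariable model is "Only factors that have statistical significance in univariate analysis will be entered for multivariate analysis". There is one exception: insulin resistance, barrier function and bacterial overgrowth "will still be considered for multivariate analysis, regardless of univariate analysis results".

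Of the 12 named factors or groups, 9 are therefore screened and 3 are exempt. SAP 4.4 gives no significance level for the screen, no model type, no correction for selection, no internal validation and no time of measurement for the three exempt factors. Treatment arm is not named as a factor. The Protocol has no competing rule.

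**The concern.** A factor gets into the final model because its estimate in these patients happened to be large relative to its standard error. The model then tests it again in the same patients, with standard errors that take the factor list as given. A factor with no effect that passes by chance carries its chance estimate forward. A real factor that passes tends to have been overestimated, and a real factor that was underestimated disappears. At stake is the list of predictors of response: which factors are on it, how strong they look, and how far their intervals can be believed.

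The exempt factors raise a second question. They stand apart from the baseline list and lack the baseline label that most of that list carries. SIBO and barrier function are also secondary efficacy parameters (SAP 4.2), insulin resistance is assessed at 1, 3 and 6 months (Protocol, Methods 4.4, item 3), and SIBO and barrier improvement are the proposed mechanism (end of Protocol Background). If on-treatment values were entered, outcomes of treatment would be presented as predictors of response.

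**Working it through.** **Inputs from the documents (SAP 3.4).** "Assuming that the rate of loss to follow up is 10%, each group will require 49 cases": 44 / (1 − 0.10) = 48.9, so 49 per group, and 49 × 4 = 196, as stated. Evaluable: 44 × 4 = 176. (Whether 44 follows from the stated formula is a separate question; it is taken as given here.) Expected responders: 44 × (0.69 + 0.44 + 0.44 + 0.10) = 44 × 1.67 = 73.5, or 41.75% of 176.

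**Assumptions, not in the documents.** The outcome is the binary effective/invalid endpoint; the model is logistic; the screen is at two-sided 0.05; each of the 9 screened groups is one variable; the 3 exempt factors are always in the model. Effect sizes and correlations are varied.

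**Chance entry.** If all 9 screened factors are useless and independent, at least one passes with probability 1 − 0.95^9 = 37%. Simulation gives 36 to 37%.

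**Chance of losing a real factor, by hand.** For one standardised continuous factor, SE(log OR) ≈ 1/√(n p(1 − p)) = 1/√(176 × 0.4175 × 0.5825) = 1/√42.8 = 0.153.

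- OR 1.3: ln 1.3 / 0.153 = 0.262 / 0.153 = 1.72. Power = Φ(1.72 − 1.96) = 0.40, so it is dropped in 60% of trials.
- OR 1.5: 0.405 / 0.153 = 2.65. Power = Φ(0.69) = 0.76, so it is dropped in 24%.
- A binary factor split 50/50 with OR 2.0 is dropped in 39%.

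These are for a factor acting alone. Other real factors or arm differences left out of the univariable model weaken its apparent effect and raise the loss.

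**Simulation of the rule** (9 screened, 3 forced in, about 176 patients):

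| Setting | Useless factor that passes: 95% CI excludes no effect | Real factors, OR 1.3 to 1.5: dropped |
|---|---|---|
| Independent factors | about 50 to 88% | about 33 to 74% |
| Correlation 0.1, several real factors | 29 to 43% | not summarised |
| Correlation 0.3, several real factors | 3 to 9% | 4 to 44% |
| No screen, all 12 factors in the model | 5 to 6% | none dropped |

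In the first row, the top of the interval range is the case with no real screened factor, and the bottom is the case with treatment arm in the model. Kept real effects are overstated by about 25 to 85% on the log odds scale.

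In the third row, at least one useless factor enters in about 65 to 94% of trials. Correlation with a real predictor gives a useless factor a genuine univariable association, so it passes often; adjustment then removes most of the association.

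**Sensitivity.** With independent factors and three real ones, the exclusion rate is 71 to 72% at a 0.05 screen, 46% at 0.10 and 24% at 0.20. At correlation 0.3 (176 to 196 patients) it is 17% if only one screened factor is real and 54% if none is, so the reassuring 3 to 9% needs several real predictors as well as correlation.

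**The case against.** A reader might infer that useless factors passing the screen will usually show intervals that exclude no effect. The documents do not support that without conditions. Liver biochemistry, lipids, BMI, fat attenuation index and life style are plausibly correlated, and with correlation 0.3 and several real predictors the final intervals are close to nominal. A looser screen, which SAP 4.4 does not rule out, also brings the figure below one half. Loss of real factors is likewise smaller when predictors correlate positively and act in the same direction. This stands, and the size must be given as a range. It does not rescue the rule: under correlation the screen lets useless factors in, so it fails to give the short, reliable list it is meant to give, and the SAP offers no means of telling which case applies.

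A reader might also infer that the plan will adjust away the pathway through which the capsules act. That goes too far. Fasting insulin and glucose, barrier function and the breath test are all measured on admission (Protocol, Prescriptions 4.2), and SAP 9.5 lists SIBO and insulin resistance among baseline indicators, so baseline values may be intended. Mechanism is also a stated objective (SAP 2.2), and Protocol, Methods 4.5 relates changes on treatment to one another in the capsule group. What stands is that SAP 4.4 does not say which values enter.

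Finally, the consequence is limited. SAP 4.4 concerns predictors; it alters neither the primary endpoint (SAP 4.1) nor the between-group comparisons (Protocol, Methods 4.4). That is correct.

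**Conclusion.** The point holds in a conditional form. Screening on significance in the same patients, without correction, makes the nominal p-values and intervals of the 9 screened factors unreliable and can drop moderate real predictors. The direction is sure; the size is not. It runs from serious distortion with roughly independent factors to nearly correct intervals with several correlated real predictors, and in the latter case the price is a model that admits useless factors in most trials. All sizes rest on the assumed 0.05 screen, logistic model, effect sizes and correlations. The three exempt factors escape the screening problem, but their measurement time needs to be stated. This should be changed, but it does not threaten the trial's main comparison.

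**What to change.** Replace the screening sentence in SAP 4.4 with a short list of factors, all entered whatever their univariable p-values.

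- **Content.** Treatment arm (assumed response runs from 10% to 69%), baseline fat attenuation index, and the baseline values of insulin resistance, barrier function and SIBO. The sponsor adds a few others from its own list.
- **Size.** Four arms take 3 parameters and the other four factors one each if barrier function is summarised in one variable: 7 in all, or 73 / 7 = 10.4 responders per parameter. Two more factors give 73 / 9 = 8.1. All 12 named candidates plus arm would give 73 / 15 = 4.9, which is why the list must be short.
- **Timing.** Fix the list now, before any outcome data by arm are examined. Database lock is too late, because the trial is open-label (SAP 3.1) and SAP 7 provides for real-time analysis of the data.
- **Reporting.** Keep the univariable results as description. Report any on-treatment values of insulin resistance, barrier function and SIBO separately, as exploratory mechanism analysis.

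The cost is SAP wording only; all the baseline measurements named are already planned. The small downside is that a few uninformative factors stay in the model.
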